7.3.4. Physical examination, vital signs

Physical examination and vital signs evaluation will be summarized by visit using frequency tables (Normal/Abnormal and not clinically significant/Abnormal and clinically significant). Shift table will be tabulated.

Systolic blood pressure, diastolic blood pressure and pulse rate will be summarized by visit in quantitative manner. Change from baseline will be calculated.

7.3.5. Ophthalmic examination

Ophthalmic examination will be summarized by visit using frequency tables (Normal/Abnormal and not clinically significant/Abnormal and clinically significant).

Protocol No: RD.03.SPR.112075 Statistical Analysis Plan Page 18 of 38 Shift table will be tabulated

Shift table will be tabulated.

7.3.6. 12-lead electrocardiogram

Results of 12-lead electrocardiogram will be summarized by visit using frequency tables (Normal/Abnormal and not clinically significant/Abnormal and clinically significant). Shift table will be tabulated.

QTc interval and change from screening will be also summarized by visit.

7.3.8. Laboratory parameters

Each hematology and biochemistry parameter will be subject to quantitative and qualitative analyses at screening and at day 19/ET.

Quantitative values in standard units will be summarized at screening and at Day 19/ET, as well as change from screening.

Frequency of subjects with low, normal, high values with respect to normal range will be summarized at screening and at day 19/ET.

Shift tables will be displayed presenting data at screening and at day 19/ET.

Each urinalysis parameter will be subject to qualitative analyses at screening and at day 19/ET. Shift tables will also be displayed.

In case of urinalysis parameter in quantitative manner, results will be presented by summary statistics.

7.4.1. Plasma concentration

Raw values of concentration of CD10367 will be summarized with geometric mean, arithmetic mean, standard deviation (SD), coefficient of variation (CV), median, minimum and maximum values by visit (day 5; day 19/ET and day 26).

Logarithmic values (ln) of concentration of CD10367 will be summarized with mean, standard deviation, median, minimum and maximum value by visit.

Protocol No: RD.03.SPR.112075 Statistical Analysis Plan Page 19 of 38

- 7.5. Analysis visit definition
- NA

8. CHANGES FROM THE PROTOCOL ANALYSIS PLAN

NA

Internally Approved 01-Feb-2019 Protocol No: RD.03.SPR.112075 Statistical Analysis Plan Page 20 of 38

CONFIDENTIAL GALDERMA

9. TABLES, FIGURES AND GRAPHS

9.1. Study subjects

Table. Enrollment by Center

Table. Subjects who discontinued treatment and reason for discontinuation

Table. Major protocol deviations

9.2. Efficacy analyses

9.2.1. Subjects characteristics

Table. Data sets analyzed

Table. Demographic data – ITT population Including age (as quantitative data and by class 18-64, 65-84 and >=85), gender, race, phototype, subject of childbearing potential.

Table. Medical history – ITT population

Including duration of psoriasis and relevant or major illnesses present before the screening visit.

Table. Previous therapies by ATC term – ITT population

Table. Previous procedures by preferred term – ITT population

Table. Concomitant therapies by ATC term – ITT population

Table. Concomitant procedures by preferred term – ITT population

Statistical Analysis Plan Page 21 of 38 9.2.2. Baseline characteristics

Table. Target location – ITT population

	CD10367 placebo pre-treated	CD10367 3% pre-treated	CD10367 placebo	CD10367 1%	CD10367 3%	Betneval 0.1%	Overall
N							
Elbows	n(%)						
Knees	n(%)						

Table. Target location – PP population

Table. Pre-treatment clinical scores in mini-zones Z1 and Z2 – ITT population

		CD10367 placebo pre-treated	CD10367 3% pre-treated	Overall
Erythema	Ν			
	2			
	3			
	4			
	Mean			
	SD			
	Median			
	(Min,Max)			
Scaling	N			
-	0			
	1			
	Mean			
	SD			
	Median			
	(Min,Max)			
Induration				
TSS				

Table. Pre-treatment clinical scores in mini-zones Z1 and Z2 – PP population

Table. Baseline clinical scores in mini-zones Z1 to Z6 – ITT population

Internally Approved 01-Feb-2019 Protocol No: RD.03.SPR.112075 Statistical Analysis Plan Page 22 of 38

CONFIDENTIAL GALDERMA

Page 22 of 38 Baseline corresponds to week 1 day 1.

Table. Baseline clinical scores in mini-zones Z1 to Z6 – PP population

Baseline corresponds to week 1 day 1.

9.2.3. Primary and secondary efficacy criteria

Table. AUC of TSS – Treatment period - PP and ITT population

		CD10367 placebo pre-treated	CD10367 3% pre-treated	CD10367 placebo	CD10367 1%	CD10367 3%	Betneval 0.1%
AUC of TSS (PP)	Ν		_				
	Mean						
	SD						
	Median						
	(Min,Max)						
AUC of TSS (ITT)	N						
	Mean						
	SD						
	Median						
	(Min,Max)						

Table. Analysis of variance for AUC of TSS – Treatment period - PP population

		LSmean(SE)	p-value*
Model Effects	Patient	-	
Treatment	CD10367 placebo pre-treated		
Treatment	CD10367 3% pre-treated		
Contrast	 CD10367 placebo – Betneval		
CCI			

Internally Approved 01-Feb-2019 Protocol No: RD.03.SPR.112075

Statistical Analysis Plan Page 23 of 38

Table. AUC of erythema – Treatment period - PP and ITT population

Table. Analysis of variance for AUC of erythema – Treatment period - PP population

Table. AUC of scaling – Treatment period - PP and ITT population

Table. Analysis of variance for AUC of scaling – Treatment period - PP population

Table. AUC of induration – Treatment period - PP and ITT population

Table. Analysis of variance for AUC of induration – Treatment period - PP population

Table. TSS and TSS percent change from day 1 – PP population

TSS		CD10367 placebo pre-treated	CD10367 3% pre-treated	CD10367 placebo	CD10367 1%	CD10367 3%	Betneval 0.1%
Screening	N						
	Mean SD						
	Median						
	(Min,Max)						
End of pre-treatment period*							
Day 1, Day 4	Ν						
	Mean						
	SD						
	Median						
Percent change from Day 1 at Day 4	(Min,Max) N						
reicent change nom Day 1 at Day 4	Mean						
	SD						
	Median						
	(Min,Max)						
Day 8, Day 11, Day 15, Day 19	N						
Percent change from Day 1 at Day	Ν						
8, Day 11, Day 15, Day 19							
	•••						

*performed only in Z1 and Z2

Internally Approved 01-Feb-2019 Protocol No: RD.03.SPR.112075

CONFIDENTIAL GALDERMA

Statistical Analysis Plan

Page 24 of 38 Table. TSS and TSS percent change from day 1 – ITT population

ITT population and with only 2 visits: Day 1 and Endpoint/LOCF

Table. Erythema and change from day 1 – PP population

 Table. Erythema and change from day 1 – ITT population

 Table. Scaling and change from day 1 – PP population

Table. Scaling and change from day 1 –ITT population

 Table. Induration and change from day 1 – PP population

Table. Induration and change from day 1 - ITT population

Table. Clearing score by visit – Treatment period - PP population

Clearing score		CD10367 placebo pre-treated	CD10367 3% pre-treated	CD10367 placebo	
Day 4	Ν				
	0				
	1				
	2				
	Mean				
	SD				
	Median				
	(Min,Max)				
Day 8, Day 11, Day 15, Day 19					

Table. Clearing score by visit – Treatment period - ITT population

Same table as above but on ITT population and with the additional visit Endpoint/LOCF

Statistical Analysis Plan Page 25 of 38

Table. Success by visit – Treatment period - PP population

Success		CD10367 placebo pre-treated	CD10367 3% pre-treated	CD10367 placebo	
Day 4	N No Yes				
Day 8, Day 11, Day 15, Day 19	N No Yes				

Table. Success by visit – Treatment period - ITT population

Table. Time to first success - Treatment period - PP and ITT population

Time to first success		CD10367 placebo pre-treated	CD10367 3% pre-treated	CD10367 placebo	
PP	N No success at any day Success at Day 19 and not before Success at Day 15 and not before Success at Day 11 and not before Success at Day 8 and not before Success at Day 4 and not before Mean SD Median (Min,Max)				
ITT					

C

Statistical Analysis Plan Page 26 of 38

Statistical Analysis Plan Page 27 of 38

Internally Approved 01-Feb-2019 Protocol No: RD.03.SPR.112075 Statistical Analysis Plan Page 28 of 38

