5.1. The Intent-to-treat (ITT) population

The ITT Population is defined as comprising all subjects who are randomized.

Protocol No: RD.03.SPR.112075 Statistical Analysis Plan Page 12 of 38

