5.2. The Per-Protocol (PP) efficacy population

This population will consist of ITT subjects, except some subjects considered as not evaluable due to major deviations from protocol.

Major deviations will be defined after data entry and before breaking the treatment blind, and may include: inclusion criteria not respected, interfering therapy, protocol deviation, poor compliance to study treatment administration or protocol requirements, unblinding. The decision on determining whether a subject is excluded from the per-protocol (PP) population will be made during the blind review meeting.

If no patient has a major deviation, PP efficacy population will be the same as ITT population, and results will be presented on the ITT population only.

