7.2.5. Efficacy analysis

7.2.5.1 Primary and secondary efficacy analysis

Descriptive statistics will be done on observed cases for PP and ITT populations.

The Area Under the Curve (AUC) will be calculated from Day 1 (before application) to Day 19 by subject and by treatment/pre-treatment on the Z1-Z6 mini-zone, using the trapezoidal rule on ITT and PP population.

Dates of theorical visit will be used to perform AUC.

AUC of TSS will be submitted to an analysis of variance including subject and treatment/pretreatment as factors in the model, ^{CCI}

AUC of individual clinical scores (erythema, scaling and induration) will be submitted to the same variance analysis.

TSS and TSS percent change from day 1 will be descriptively summarized by visit, as the individual score of erythema, scaling and induration and their respective change from day 1. The analysis will be performed on PP population and ITT population (baseline and Endpoint/LOCF) Success will be presented in frequency tables (N,%) by treatment/pre-treatment and by visit. The time to first success will be summarized by treatment/pre-treatment.

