7.2.6.2 Handling of dropouts or missing data

For evaluation by visit, on ITT population, a last visit named "Endpoint/LOCF" containing the last observation carried forward (LOCF) will be created.

For Area Under the Curves (of the TSS or for each individual clinical score), no imputation for missing assessment will be done and calculations will be done on observed data, nevertheless for the subjects who terminated earlier, the Final Visit will be imputed to the closest theoretical visit of the protocol.

For patients who have individual score assessments on unscheduled day, closest theoretical visit of the protocol will be used, for each evaluation overtime and AUC.

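### Early terminators' raw AUCs cover fewer days than completers', so primary endpoint values are not comparable; secondarily, every visible ANOVA table of AUC is labelled PP

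*SAP*

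**What the plan says.** The primary criterion is the AUC of TSS from Day 1 to Day 19 (protocol 7.1.2.1, SAP 4.1), with scores on Days 1, 4, 8, 11, 15 and 19. SAP 7.2.5.1 calculates it "using the trapezoidal rule on ITT and PP population", on theoretical visit dates.

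For missing data, SAP 7.2.6.2 says of the AUC that "no imputation for missing assessment will be done and calculations will be done on observed data", and that "for the subjects who terminated earlier, the Final Visit will be imputed to the closest theoretical visit of the protocol". In that section LOCF is stated only for evaluation by visit. No carry-forward to Day 19 and no division by days observed is visible for the AUC.

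On populations, SAP 5.1 states: "The ITT Population is defined as comprising all subjects who are randomized". SAP 7.2.5.1 submits AUC to an ANOVA with subject and treatment/pre-treatment as factors. The visible words name no population for that model, and the sentence runs into a redaction. In SAP 9.2.3 the descriptive AUC tables are for PP and ITT; the TSS shell shows N, mean, SD, median and range. The ANOVA tables are titled "Analysis of variance for AUC of TSS – Treatment period - PP population" and, for example, "Analysis of variance for AUC of erythema – Treatment period - PP population"; scaling and induration follow the same pattern. If no subject has a major deviation, SAP 5.2 says "results will be presented on the ITT population only".

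**The concern.** A lower AUC should mean less disease. Under the stated rule it can also mean less observation, because the area stops accumulating when the subject leaves. An unchanged zone in an early terminator can then score better than an improving zone in a completer. The descriptive AUC tables would mix values from different windows, and any ANOVA that includes such a subject would count only part of that subject's treatment difference.

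The second issue is separate. Protocol 2.2 hypothesises significant superiority over vehicle. In the visible table list, no standard error or p-value for that hypothesis uses all randomised subjects. A reader could set ITT means beside PP means but could not judge the precision of the ITT differences.

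**Working it through.** The plan states no figure for this effect. The documents supply the scoring days, the 18-day window (19 − 1), N = 24 and the entry minimum TSS of 6 for non-desquamated zones. The number and day of exits, the SD and the shape of the effect over time are assumptions.

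**1. Window and level.** With the last mapped scoring visit at Day v, the span is s = v − 1. A flat TSS of 6 gives AUC = 6s.

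| Last visit | s (days) | AUC, flat TSS 6 |
|---|---|---|
| Day 4 | 3 | 18 |
| Day 8 | 7 | 42 |
| Day 11 | 10 | 60 |
| Day 15 | 14 | 84 |
| Day 19 | 18 | 108 |

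A completer improving linearly from 6 to 3 has AUC 4.5 × 18 = 81, which looks worse than the unchanged zone cut at Day 8 (42). Under nearest-visit mapping, termination on Day 18 maps to Day 19 and gets the full window, Day 17 ties between Days 15 and 19, and Day 2 maps to Day 1, which leaves no trapezoid.

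**2. Descriptive tables, one Day 8 exit in 24.** Take completers with mean AUC 108.
- Mean = (23 × 108 + 42)/24 = 105.25, a fall of 2.5%.
- SD = √[(22 × sd² + (23/24) × 66²)/23], where 66 = 108 − 42. For completer SDs of 10, 20 and 30 this gives 16.6, 23.8 and 32.3.

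**3. ANOVA contrast.** All six zones of a subject are cut at the same visit. With complete zones, the subject-plus-treatment contrast is the mean of the within-subject differences, so a loss of area common to all six zones cancels. What does not cancel is the missing part of the difference itself. The share of the full AUC difference retained is s/18 if the difference is constant over time and (s/18)² if it grows linearly from zero at Day 1. The loss with one exit in 24 is (1 − share)/24.

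| Exit | Share, constant | Share, linear | Loss, constant | Loss, linear |
|---|---|---|---|---|
| Day 4 | 0.167 | 0.028 | 3.47% | 4.05% |
| Day 8 | 0.389 | 0.151 | 2.55% | 3.54% |
| Day 11 | 0.556 | 0.309 | 1.85% | 2.88% |
| Day 15 | 0.778 | 0.605 | 0.93% | 1.65% |

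The range is 0.9% to 4.1% per exit. Losses add: Day 8 exits cost 5.1% to 7.1% for two subjects and 7.6% to 10.6% for three. With no exits the loss is 0%.

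**4. What the remedies leave, per exit in 24.**
- AUC × 18/s returns the flat Day 8 exit to 42 × 18/7 = 108. The loss is 0% for a constant effect. For a linear effect the share becomes s/18, so 3.47%, 2.55%, 1.85% and 0.93% remain for Days 4, 8, 11 and 15.
- Carrying the last score to Day 19 also leaves 0% for a constant effect. For a linear effect the share is [s²/2 + s(18 − s)]/162, so 2.89%, 1.56%, 0.82% and 0.21% remain.

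**5. Population labels.** Of the four ANOVA titles visible in SAP 9.2.3, four say PP and none says ITT. The redaction follows the TSS shell. The titles for erythema, scaling and induration run without a break and contain no ITT ANOVA.

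**The case against.** The effect on the contrast is small, runs towards no effect and vanishes without early exits. It may not reach the PP ANOVA at all: SAP 7.2.4 removes subjects with low compliance from PP, and a Day 8 exit would have had 5 or 6 of 14 applications. That stands, but no compliance threshold is given and early termination is not itself a listed exclusion in SAP 5.2, so removal is plausible rather than assured. The ITT description is affected either way.

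The remedy is also partial, and dividing by days observed alone would turn the criterion into a mean over a variable window. That is why the value should be rescaled to 18 days and labelled as such.

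On populations, the objection is stronger. The evidence for TSS is a table shell next to redactions. Protocol 9.1.2 assigns by-visit efficacy to PP, gives ITT a Baseline and Endpoint/LOCF summary for TSS and scores, and names no population for AUC. A PP emphasis in an exploratory Phase 2a trial is therefore a choice to justify and does not contradict the protocol. The point disappears if there are no major deviations.

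Three stronger readings are tempting and not supported:
- **Shortened AUCs favour one treatment.** Early termination cuts all six zones alike, and zones stopped for poor local tolerance continue to be scored (protocol 7.1.1.1).
- **PP exclusions unbalance the treatments.** Exclusions are decided per subject at a blind review and remove all six zones together. What can be lost is subjects and breadth of population.
- **The plan has no ITT inference for the primary endpoint.** The redactions prevent that conclusion for TSS.

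**Conclusion.** The main point holds. The rule in SAP 7.2.6.2 gives values of the primary endpoint that are not comparable between early terminators and completers. The distortion is plain in the descriptive tables (42 against 108 for the same unchanged score) and modest in the ANOVA. The ANOVA figures assume that all six zones are scored up to exit and that the exiting subject follows the same effect course until then. They cover two illustrative effect shapes and are not bounds. The documents give no number of early exits.

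The population point holds for the visible text only, with more certainty for the three individual scores than for TSS. Its size cannot be calculated, because the number of PP exclusions is not given. Both changes should be made, mainly because they cost little.

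**What to change.** **SAP 7.2.6.2.** State that, for subjects with at least one post-baseline score, AUC is divided by the days from Day 1 to the last scored scheduled visit and multiplied by 18, and is reported as a rescaled Day 1 to Day 19 AUC. Completers' values do not change. Add a sensitivity analysis that carries the last score to Day 19 for all randomised subjects, and say how subjects with only a Day 1 score are treated.

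**SAP 7.2.5.1 and 9.2.3.** Name the population for the ANOVA. Run the same subject-plus-treatment model on ITT beside PP, for TSS (if the redacted text does not already do so) and for each individual score. Show LS-mean contrasts with 95% CIs and include zones whose applications were stopped.

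**Cost.** Two derived variables, up to four more tables from the same model, and no new data. Rescaling assumes that the average over the observed days applies up to Day 19; if the effect grows, the 0.9% to 3.5% per exit shown above remains. In the sensitivity analysis a subject with only a Day 1 score enters with about zero effect, which shrinks the contrast by 1/24 = 4.2%. The ITT estimate may be smaller than the PP estimate.

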9.3. Safety analyses

9.3.1. Extent of exposure

Table. Pre-treatment duration of keratolytic product – Safety population

		CD10367 placebo	CD10367 3%
		pre-treated	pre-treated
Number of days of keratolytic product applications	Ν		
	4		
	5		
	6		
	7		
	Ν		
	Mean		
	SD		
	Median		
	(Min,Max)		

Statistical Analysis Plan Page 29 of 38

Table. Study drug applications during the treatment period on mini-zones Z1 to Z6 - Safety population

	CD10367 placebo pre-treated	CD10367 3% pre-treated	CD10367 placebo		
Ν					
No					
Yes					
Ν					
No					
Yes					
N Temporarily discontinued due to irritation Permanent discontinuation due to irritation Other					
	No Yes N No Yes N Temporarily discontinued due to irritation Permanent discontinuation due to irritation	placebo pre-treated N No Yes N No Yes N Temporarily discontinued due to irritation Permanent discontinuation due to irritation	placebo pre-treatedNNoYesNNoYesNTemporarily discontinued due to irritationPermanent discontinuation due to irritation	placebopre-treatedNNoYesNNoYesNTemporarilydiscontinued dueto irritationPermanentdiscontinuationdue to irritation	placebo pre-treatedpre-treatedNNo YesNNo YesNTemporarily discontinued due to irritationPermanent discontinuation due to irritation

Table. Number of applications during the treatment period on mini-zones Z1 to Z6 – Safety population

	CD10367 placebo pre-treated	CD10367 3% pre-treated	CD10367 placebo	
Ν				
11				
12				
13				
Mean				
SD				
Median				
(Min,Max)				

Statistical Analysis PlanPage 30 of 38**9.3.2.**Local tolerance

Table. Irritation in term of continuous data

Irritation	CD10367 placebo pre-treated	CD10367 3% pre-treated	CD10367 placebo			
Day 2						
Ν	XX	XX	XX	XX	XX	XX
Mean±sd Median	xx.x±xx.x	xx.x±xx.x	xx.x±xx.x	xx.x±xx.x	XX.X±XX.X	XX.X±XX.X
(Min,Max)	xx.x (xx.x, xx.x)	XX.X (XX.X, XX.X)	xx.x (xx.x, xx.x)	XX.X (XX.X, XX.X)	xx.x (xx.x, xx.x)	xx.x (xx.x, xx.x)
Day 3						
Day 19						
Day 19/ET						
Follow-up						

0= None - 1=Mild - 2=Moderate - 3=Severe

Table. Irritation in term of frequency distribution

Irritation		CD10367 placebo pre-treated	CD10367 3% pre-treated	CD10367 placebo	
Day 2	N 0- None				
	1- Mild				
	2- Moderate				
	3 – Severe				
Day 2					

Table. Stinging /Burning in term of continuous data

Table. Stinging /Burning in term of frequency distribution

Table. Pruritus in term of continuous data

Table. Pruritus in term of frequency distribution

Table. Worst Score in term of frequency distribution

Internally Approved 01-Feb-2019 Protocol No: RD.03.SPR.112075 Statistical Analysis Plan Page 31 of 38

9.3.3. Adverse events

Table. Overview of adverse events during the pre-treatment period – Safety population Table. Listing of adverse events during the pre-treatment period – Safety population Table. Listing of adverse events prior the pre-treatment period – Safety population †Or listing if few AE. Table. Overview of adverse events during the treatment period – Safety population Table *†*. Summary of adverse events by Preferred Term – Safety population Table †. Summary of adverse events Related to the study drug by Preferred Term – Safety population Table †. Summary of adverse events Related to the protocol procedure by Preferred Term – Safety population Table †. Summary of adverse events Related to the study by Preferred Term – Safety population Table . Summary of adverse events by System Organ Class and Preferred term – Safety population Table †. Summary of adverse events Related to the study drug by System Organ Class and Preferred term – Safety population Table †. Summary of adverse events Related to the protocol procedure by System Organ Class and Preferred term – Safety population Table †. Summary of adverse events Related to the study by System Organ Class and Preferred term – Safety population Table †. Summary of adverse events by severity by System Organ Class and by Preferred term – Safety population Table †. Summary of adverse events Related to the study drug by severity by System Organ Class and by Preferred term – Safety population Table †. Summary of adverse events Related to the protocol procedure by severity by System Organ Class and by Preferred term – Safety population Table †. Summary of adverse events Related to the study by severity by System Organ Class and by Preferred term – Safety population Table †. Summary of serious adverse events by System Organ Class and by Preferred term – Safety population Table †. Summary of adverse events leading to discontinuation by System Organ Class and by Preferred term – Safety population

Table †. Summary of AESIs by System Organ Class and by Preferred term – Safety population

Statistical Analysis PlanPage 32 of 38**9.3.4.**Vital Signs, Physical Findings

Table. Physical examination – Safety population

		Screening	DAY 19/ET
Physical examination	Ν		
	Normal		
	Abnormal and Not clinically significant		
	Abnormal and Clinically significant		

Table. Shift table of Physical examination – Safety population

	Day 19/ET		
Screening	Normal	Abnormal and not clinically significant	Abnormal and clinically signficant
Normal			
Abnormal and not clinically significant Abnormal and clinically			
signficant			

Table. Vital signs – Safety population

		Screening	Baseline	D19/ET	Change from baseline
Systolic blood pressure (mmHg)	Ν				
	Mean				
	SD				
	Median				
	(Min,Max)				
Diastolic blood pressure (mmHg)					
Pulse rate (bpm)					
Vital signs evaluation	Ν				
	Normal				
	Abnormal and Not clinically significant				
	Abnormal and Clinically significant				

Page 33 of 38

Table. Shift table of vital signs evaluation – Safety population

	Day 19/ET		
Baseline	Normal	Abnormal and not clinically significant	Abnormal and clinically signficant
Normal			
Abnormal and not clinically significant			
Abnormal and clinically signficant			

Table. Ophthalmic examination – Safety population

Table. Shift table of ophthalmic examination - Safety population

Table. 12-lead ECG – Safety population

		Screening	DAY 19/ET
ECG	N		
	Normal		
	Abnormal and Not clinically significant		
	Abnormal and Clinically significant		
QTC (ms)	Ν		
	Mean		
	SD		
	Median		
	(Min,Max)		
QTC > 500 ms	Ν		
	No		
	Yes		
Change in QTC (ms)	Ν		
	Mean		
Change > 60 ms	N No Yes		

Table. Shift table for 12-lead ECG – Safety population

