6.1.5.1 Selection of target plaque(s) and mini-zones

During Baseline visit, validation of the stability of the psoriatic plaques selected at Screening will be checked by the Investigator.

At Baseline visit, the selected target mini-zones for standard psoriatic skin conditions (n=4) should:

- be located on the upper and/or lower extremities (anterior crest of tibia, apex of knees and apex of elbows excluded) and/or on the trunk. Plaques on the face, scalp, hands, feet and folds will not be eligible as test areas.
- have a Total Sum Score (TSS = erythema + induration + scaling) ≥ 6; each item separately being ≥ 2 (see Table 5),
- have identical severity (i.e. identical baseline TSS or variation of ± 1 grade),
- be approximately 2 cm in diameter and be at least 2 cm apart from each other in order to avoid any interference between products.

Target mini-zones previously selected at Screening visit for desquamated psoriatic skin conditions (n=2) should at Baseline visit:

- be located on the upper and/or lower extremities (anterior crest of tibia, apex of knees and apex of elbows excluded) and/or on the trunk. Plaques on the face, scalp, hands, feet and folds will not be eligible as test areas.
- have a scaling score of 0 or 1,
- have identical severity between the two zones or variation of ±1 grade for the sum of induration and erythema scores, each item separately being ≥2
- are approximately 2 cm in diameter and at least 2 cm apart from each other.

If the scaling score is not at 0 or 1 after 2 weeks of pre-treatment period, they will not be randomized in the study.

Protocol No.: RD.03.SPR.112075 V01 16 Aug 2016

Page 43 of 85

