6.3.3 Dispensing and return

Each subject will receive the keratolytic and the emollient products at Screening visit.

Subjects will be instructed by the investigator on the importance of being compliant with the use of the keratolytic product throughout the week(s) proceeding Baseline visit.

From Baseline, no drug will be dispensed directly to the subject.

As this study is an Investigator/evaluator blinded study, the Investigator should not have access to the study drugs. The person in charge of product applications will not be the Investigator/evaluator.

In the event of Screen failure (e.g. due to abnormal laboratory results), the Investigator or designee must immediately instruct the subjects to stop the keratolytic product regimen.

In the event of early termination/suspension of the clinical trial, a rapid recall of study drug(s) to Galderma will be initiated

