9.1.2 Populations analyzed and evaluability

The intent-to-treat efficacy population (ITT) consists of the entire randomized population.

The ITT population will be analyzed for TSS, clinical scores and their percent change and change from baseline. A last visit for treatment period will be created, Endpoint, containing the last observation carried forward LOCF. Only Baseline and Endpoint/LOCF will be descriptively summarized

The per-protocol efficacy population (PP) consists of all randomized subjects, except some subjects considered as not evaluable due to major deviations from the protocol.

Major deviations will be defined after data entry and before breaking the treatment blind, and may include: inclusion criteria not respected, interfering therapy, protocol deviation, poor compliance to study treatment administration or protocol requirements, unblinding. The decision on determining whether a subject is excluded from the PP population will be made during a blind review meeting.

The per-protocol population as defined above will be analyzed for efficacy at each evaluation visit during treatment period.

All Subjects having received a treatment at least once will be included in the safety population.

If applicable, an additional safety population will be defined for the pretreatment period with keratolitic.

Protocol No.: RD.03.SPR.112075 V01 16 Aug 2016

Page 74 of 85

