5.3. The Safety population

Safety population corresponds to all subjects who received at least once the study treatment during the treatment period.

In case of identical populations, only one safety population will be used for the analysis.

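### The pre-treatment adverse event and keratolytic exposure outputs, as titled, use a Safety population that requires study drug, so subjects who used the keratolytic but were never randomised are left out

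*SAP*

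**What the plan says.** SAP 5.3 defines the set: "Safety population corresponds to all subjects who received at least once the study treatment during the treatment period". SAP 7.3 then bases all safety summaries on the safety population.

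Three outputs that describe the keratolytic phase carry that label:
- the exposure table in SAP 9.3.1, "Pre-treatment duration of keratolytic product – Safety population", whose only columns are the two pre-treated study-drug zones (placebo and CD10367 3%);
- the adverse event table in SAP 9.3.3, "Overview of adverse events during the pre-treatment period – Safety population";
- the matching listing in SAP 9.3.3.

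A further listing, of events that begin before pre-treatment, has the same label.

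Protocol 9.1.2 had provided for something else: "If applicable, an additional safety population will be defined for the pretreatment period with keratolitic". SAP 5.3 also has the sentence "In case of identical populations, only one safety population will be used for the analysis". The visible SAP contains no second definition, and SAP section 8 declares no change from the protocol analysis.

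On who may use the keratolytic without reaching study drug, protocol 6.3.3 has it handed out at Screening. For screen failures, the investigator or designee "must immediately instruct the subjects to stop the keratolytic product regimen". Protocol 6.1.5.1 says of subjects whose scaling is still above 1 after two weeks of pre-treatment that "they will not be randomized in the study".

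**The concern.** The keratolytic is used at home before Day 1, and study treatment starts on Day 1. A population defined by study treatment therefore selects, from everyone exposed to the keratolytic, only those who went on to randomisation and a first application. For a summary of what happened during keratolytic use, that conditions the denominator on an event that comes after the exposure.

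Two things are at stake. The exposure table and the event overview do not describe all exposed subjects. And the listing drops those subjects' events altogether, although protocol 9.1.3 says that events before Baseline will be listed and states no such restriction. Safety is part of the primary objective, and protocol 7.2.6.1.7 names the keratolytic among the procedures for which the investigator must assess causality.

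**Working it through.** **Step 1. Can a subject use the keratolytic and not be in the Safety population?** Set side by side:
1. Dispensing is at Screening (protocol 6.3.3); randomisation and the first study-drug application are at Day 1 (protocol 8.1.2).
2. Scaling not at 0 or 1 after two weeks of use bars randomisation (protocol 6.1.5.1).
3. Screen failures, with abnormal laboratory results as the example, are told to stop the keratolytic (protocol 6.3.3).
4. The ECG and the ophthalmic examination both decide eligibility and may take place during pre-treatment (protocol 8.1.1).

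So yes. Such a subject has keratolytic exposure and possibly adverse events, but no study treatment, and does not meet SAP 5.3.

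**Step 2. The plan's own figure.** Inputs from protocol 5.1: 24 randomised, screen failure rate about 40%.
- Screened = 24 / (1 − 0.40) = 40, which agrees with the stated 40.
- Not randomised = 40 − 24 = 16.

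**Step 3. Share of keratolytic users omitted.** Let k be the number of the 16 who applied the keratolytic at least once. The documents do not give k, so the whole range is shown. All 24 randomised subjects are assumed to have used the keratolytic and received study drug. Omitted share = k / (24 + k).

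| k (assumed) | Keratolytic users | Omitted |
|---|---|---|
| 0 | 24 | 0% |
| 4 | 28 | 14.3% |
| 8 | 32 | 25.0% |
| 12 | 36 | 33.3% |
| 16 | 40 | 40.0% |

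**Step 4. Direction of the effect on an event rate.** Let a be the number of the 24 with an event and b the number of the k omitted subjects with one. The table shows a/24; the rate among all users is (a + b)/(24 + k). The table understates when b/k exceeds a/24 and overstates when b/k is below it. Assumed example with a = 2 and k = 4, so that the table shows 2/24 = 8.3%:
- all four omitted subjects had an event: 6/28 = 21.4%, so the table understates;
- none of the four had an event: 2/28 = 7.1%, so the table slightly overstates.

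**Step 5. Chance of seeing an event at all.** For an assumed event rate of 5% per subject, P(at least one) = 1 − 0.95^n. This is 70.8% for n = 24 and 87.1% for n = 40, the upper bound.

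**The case against.** Four points can be made against this.

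*Removed text.* The sentence in SAP 5.3 on identical populations has nothing to compare if only one safety population exists. Together with protocol 9.1.2, it suggests that a second set was defined and then removed from the public version. SAP 7.2.1 also has a redacted item directly after the safety population in its list. A reader might infer that the sponsor forgot the pre-treatment set; the documents do not support that. One could go further and read the label on the pre-treatment tables as meaning the matching set. The visible text cannot rule this out for the adverse event outputs. It fits poorly with the exposure table, whose columns are zones that exist only for randomised subjects, and with SAP 7.3, which refers to one safety population. What stands is that the titles are at best ambiguous and, read literally, point to the study-drug set.

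*Direction.* A reader might infer that keratolytic event rates are biased downward because those who stop for irritation drop out. The reasons the protocol gives for non-randomisation here are persistent scaling and, as an example, laboratory results. Neither is a keratolytic adverse event, and step 4 shows that the error can go either way. This objection stands.

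*Size.* Sixteen is a ceiling. Screening can run up to three weeks before pre-treatment, and protocol 8.2 starts the keratolytic seven days before the planned Baseline visit, so many failures may be found before first use. This also stands: k could be close to 0.

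*Consequence.* The objective concerns CD10367, not a marketed cosmetic, and no comparison uses a keratolytic event rate. Events are collected from consent, those judged related are followed, and serious events go to the sponsor within 24 hours. This limits the point to tabulation and listing. It does not remove it, because the SAP has chosen to produce these outputs.

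**Conclusion.** The point holds as a reporting gap. On the visible text, the keratolytic duration table and the pre-treatment adverse event overview and listing leave out subjects who used the keratolytic but never received study drug, and no visible title uses the additional population that protocol 9.1.2 provides for.

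The number omitted is unknown: 0 to 16 subjects, or 0% to 40% of keratolytic users, if 40 are screened, 24 are randomised, and all 24 use the keratolytic and receive study drug. Rates in these tables are conditional on reaching study drug. They are understated if subjects stop because of keratolytic events, and may be slightly overstated otherwise. The gap between 8.3% and 21.4% in the working rests on assumed counts and is not an estimate.

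The point does not show that adverse events go uncollected, and it does not touch the treatment-period results for CD10367.

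**What to change.** Use a pre-treatment safety population of all subjects with at least one keratolytic application, randomised or not. If the full SAP has no such set, define it in SAP 5.3. If it already has one, name it in the table titles.

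Apply it to the keratolytic duration table in SAP 9.3.1 and to the pre-treatment adverse event overview and listing in SAP 9.3.3. Present these in one overall column, since zone columns have no meaning for subjects who were never randomised. Make the sentence on safety data in SAP 7.3 agree. Keep the current Safety population for all treatment-period tables.

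The cost is a few changed titles and denominators. Adverse events are already collected from consent, so no new adverse event collection is needed. Taking the listing of events that precede pre-treatment from all consented subjects is optional.
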